6.5 THE TREATMENT LASER SYSTEM

In this study we will use a Modulight laser (ML7710-665). This is a medical laser designed for PDT. This laser system can deliver the light fluence rate (W/cm^2) and dose (J/cm^2) at the wavelength (665 ± 3 nm) required to activate the HPPH. The laser system includes a calibration port, and a SanDisk memory card for storing device history data. The PDT center at RPCI purchased this laser model for research evaluation.

The participating sites will use the same laser model and identical treatment fibers.

7 TREATMENT PLAN FOR PDT WITH HPPH:

7.1 DOSING AND ADMINISTRATION

For participants randomized to HPPH with PDT, the light and drug dose will be fixed, 150 mW/cm^2 to deliver 140 J/cm^2 of 665-nm light and 4 mg/m^2 drug, respectively. The HPPH product will be added to 100 cc intra venous (i.v.) bag of D5W and infused via i.v. pump over 1 hr.

The justifications for selecting these doses are provided in sections 1.4.1 and 1.5.1. Treatment will be administered in an outpatient basis in most cases. Reported adverse events (AEs) and potential risks are described in **Section 10.1**.

7.2 PARTICIPANT DOSE MODIFICATIONS

The drug dose and light dose will not be modified.

7.3 DURATION OF TREATMENT

Participants may remain on study in the absence of disease progression, unacceptable toxicity or withdrawal from study.

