7.4 STUDY WITHDRAWAL

Upon participant withdrawal from the study, all end of study evaluations and tests will be conducted. All participants who discontinue due to an AE must be followed until the event resolves or stabilizes. Appropriate medical care should be provided until signs and symptoms have abated, stabilized, or until abnormal laboratory findings have returned to acceptable or pre-study limits. The final status of the AE will be reported in the participant's medical records and the appropriate eCRF.

Reasons for study withdrawal should be classified as follows:

- Death.
- Progressive disease.
- Treatment-related toxicity.
- Toxicity unrelated to treatment.
- Investigator judgment.
- The Investigator may withdraw a participant if, in his/her judgment, it is in the participant's best interest to do so.
- Participant receives an additional adjuvant therapy.
- Noncompliance
- Participant voluntary withdrawal
- A participant may withdraw from the study at any time, for any reason. If a participant discontinues treatment, an attempt should be made to obtain information regarding the reason for withdrawal.
- Participants in which the surgical pathology demonstrates perineural invasion, extracapsular spread or the participant requires additional therapy including radiation or chemotherapy.

Participants who are unavailable for follow-up evaluations should be classified as lost to follow-up for 1 of the following reasons:

- Lost to follow-up: For a participant to be considered lost to follow-up, the investigator must make two attempts to re-establish contact with the participant. The attempts to re-establish participant contact must be documented (e.g., certified letter).
- Death: Date and cause of death will be recorded for those participants who die within 30 days after last dose of study drug (telephone contact with family is acceptable).

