12.2 SAMPLE SIZE DETERMINATION

In the proposed randomized trial, participants will be randomized to the treatment arms using a stratified block randomization scheme, with blocking stratified by clinical site (RPCI, and two other participating sites). Participants will be included in data analyses according to their randomized treatment assignment irrespective of the treatment actually received (intent-to-treat). Exceptions would include those who withdraw their consent to use any of their data prior to receiving any study medication. Initiation of study treatment will take place as soon as possible following randomization. No method of imputation will be used for missing data. All available data from participants who fail to complete this study will be included in all safety summaries.

The safety of the interventions will be assessed through the evaluation of Grade 3 or higher toxicities deemed possibly related to treatment. Both efficacy (e.g., tumor response) and toxicity rates will be estimated using simple relative frequencies. The corresponding 95% confidence intervals for the estimated probabilities will be computed using the method proposed in Clopper and Pearson (1934).

The design for this study is based on a test for non-inferiority of PDT compared to standard of care with regards to tumor response at 24 months post-procedure. Justification for use of a non-inferiority trial is that PDT may be viewed as a potential replacement for standard of care if it is established as less toxic than the standard of care yet still providing acceptable efficacy. Let π_{SOC}

and π_{PDT} are the probabilities of tumor response in the standard of care and PDT groups, respectively. The hypotheses corresponding to the proposed non-inferiority trial are

$$H_0 : \pi_{PDT} \leq \pi_{SOC} - \Delta,$$
$$H_a : \pi_{PDT} > \pi_{SOC} - \Delta,$$

where Δ is the non-inferiority margin. Specifically, we will be using the approach of Farrington-Manning to test our hypothesis via a score based test.⁵³

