Under the null hypothesis ($\pi_{PDT} = \pi_{SOC} - \Delta = \pi$) is the probability of observing a particular set of results. A non-inferiority margin of 20 percentage points will be utilized and the Farrington-Manning based test will be performed in conjunction with a 0.05 nominal significance level. In the event that the non-inferiority test is statistically significant, a test for superiority will be conducted. The samples sizes of the trial are set at 57 in the standard of care and PDT groups. With the proposed sample sizes, there is approximately 80% power associated with the non-inferiority test when the true tumor response probabilities are equal to 85% in both groups. The calculation was carried forth using SAS PROC POWER.

In the analysis of QoL simple data analyses will initially take place including individual participant-level profile plots and overall mean plots used to examining the mean structure. Formal statistical examination of longitudinal patterns will be done through the use of a mixed model. Restricted maximum likelihood estimation will be utilized in the model fitting procedures as implemented by SAS PROC MIXED (version 9.3). Once the model is fit, specific linear contrasts based on the estimated model parameters will be constructed and used to test hypotheses concerning between time points and between group comparisons. We acknowledge the possibility of informative missingness, that is, the probability of a particular observation being missing may be related to the health of the participant, and therefore analyses will be interpreted with caution. All tests will be two-sided and tested at a 0.05 nominal significance level. Standard diagnostic plots will be used to assess model fit and transformations of variables may be considered in order to meet statistical assumptions.

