12.3 EFFICACY ANALYSIS

Objective tumor response will be tabulated overall. All participants who will be randomized to the PDT treatment or surgery will be evaluable for response. Tumor response will be evaluated according to RECIST v1.1. The treating physician will examine the clinical response and a photograph of the treatment site/s will be taken with paper ruler, to determine the reduction in the lesion size. Tumor response will be determined according to the guidelines in sections 9.2 and 9.3.

If clinically indicated, the clinical evaluation will be confirmed with pathological examination of tissue 3-mm punch biopsy that will be taken from the treated region.

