Appendix E Toxicity Serious Adverse Event Reports

An evaluation of toxic response to HPPH administration will be performed on all participants treated under this protocol. Responses will be graded based upon the classification criteria listed in the Common Terminology Criteria for Adverse Events, Version 4.0.

The following scale will be used for systemic toxicity:

Description	Grade
Acceptable	Grade 0, Grade 1, Grade 2
Unacceptable	Grade 3 or higher

Adverse events will be graded and recorded in the electronic database. Serious Adverse Events will be reported on the SAE Reporting Form.

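### Sections 7.3 and 7.4 let participants leave the study after a one-time treatment, and no rule follows them to the 24-month primary response or says how their exit assessment counts

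*Combined protocol and SAP*

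**What the plan says.** All references are to the combined protocol and SAP.

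- **Treatment.** Section 4.1.1 gives one HPPH infusion with illumination about a day later. The comparator is one operation (Section 8.4). After that, no study treatment remains to be stopped.
- **Staying on study.** Section 7.3: "Participants may remain on study in the absence of disease progression, unacceptable toxicity or withdrawal from study".
- **Leaving the study.** Section 7.4 lists related toxicity, unrelated toxicity, investigator judgment and noncompliance among the reasons for study withdrawal. It also provides: "Upon participant withdrawal from the study, all end of study evaluations and tests will be conducted". A participant who stops because of an adverse event is then followed until that event settles.
- **Primary endpoint.** Sections 3.1, 4.1.2, 12 and 12.2 place tumor response at 24 months. Section 12.3: "All participants who will be randomized to the PDT treatment or surgery will be evaluable for response".
- **Analysis rule.** Section 12.2 specifies intent-to-treat. Its only named exception is withdrawal of consent to data use before study medication. It adds: "No method of imputation will be used for missing data".
- **Outcome rules near by.** Section 4.3 counts progression, local recurrence, and partial or no response after PDT as treatment failures. Section 9.3 counts symptomatic deterioration as progression only when it is unrelated to study treatment. Neither covers an exit for treatment toxicity, noncompliance or investigator judgment.

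**The concern.** The two sections do not distinguish the end of treatment from the end of follow-up. In a trial of a single procedure, an exit for toxicity cuts short only the observation that the primary analysis needs. An evaluation at week 6, say, is not a response at 24 months.

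Two readings are then open. The participant may have no primary outcome and drop out of the denominator, which conflicts with Section 12.3. Or the exit finding may stand in for month 24, so that an early complete response counts as a durable one. Section 9.3 leaves room for the second reading: it defines a best overall response up to the time the participant goes off study, and does not say whether that feeds the primary comparison.

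The loss could differ by arm. Section 7 is headed as the PDT treatment plan. The only scale that labels toxicity unacceptable is in Appendix E, which is written for one arm: "An evaluation of toxic response to HPPH administration will be performed on all participants treated under this protocol". Treatment assignment is known to everyone. In a non-inferiority comparison, selective loss of late failures in the PDT arm would favor the claim.

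**Working it through.** **Inputs.** 57 per arm, margin 20 points and 85% response in both arms (Section 12.2). At most 114 enrolled (Section 4.4), which is 2 × 57. No dropout rate appears anywhere, so every loss rate below is an assumption.

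**Sidedness.** Section 12.2 says only that the "Farrington-Manning based test will be performed in conjunction with a 0.05 nominal significance level". In the quality-of-life paragraph it says: "All tests will be two-sided and tested at a 0.05 nominal significance level". I read the non-inferiority test as one-sided 0.025 and show one-sided 0.05 beside it.

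**Reproducing the stated power.** The plan says "there is approximately 80% power associated with the non-inferiority test when the true tumor response probabilities are equal to 85% in both groups". Power by normal approximation is

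Φ[(0.20 − z × s0) / s1].

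Here s0 uses the Farrington-Manning constrained estimates (0.708 for PDT, 0.908 for surgery) and s1 uses 0.85 in both arms.

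- s0 = √[(0.708 × 0.292 + 0.908 × 0.092) / 57] = 0.0714
- s1 = √[2 × 0.85 × 0.15 / 57] = 0.0669
- (0.20 − 1.96 × 0.0714) / 0.0669 ≈ 0.90, so power is 81.5%

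This agrees with about 80%. At one-sided 0.05 the same formula gives 89.1%, so one-sided 0.025 is the closer match. The smallest size reaching 80% at one-sided 0.025 is 55 per arm, so only 57 − 55 = 2 per arm can be lost.

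**Equal loss in both arms, lost participants left out.**

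| Assumed loss | Assessed per arm | Power, one-sided 0.025 | Power, one-sided 0.05 |
|---|---|---|---|
| 0% | 57 | 81.5% | 89.1% |
| 5% | 54 | 79.3% | 87.6% |
| 10% | 51 | 76.9% | 85.8% |
| 15% | 48 | 74.3% | 83.8% |
| 20% | 46 | 72.4% | 82.4% |

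**Loss in the PDT arm only.** By exact enumeration of the score test at one-sided 0.025, power is 83.2% with 57 against 57, 81.6% with 54 against 57, and 79.5% with 51 against 57.

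**Room to enroll more.** Keeping 57 assessed per arm at 10% loss needs 57 / 0.9 = 63.3, so 64 per arm or 128 in all, above the cap of 114.

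**If exits are counted as non-response instead.** At an assumed 10%, the observed rate is 0.85 × 0.90 = 76.5%. Power at one-sided 0.025 is 70.6% if both arms lose equally and 33.7% if only PDT does. The unstated counting rule therefore matters more than the lost numbers.

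**Worst case for bias.** Suppose 37 of 57 PDT participants truly respond (64.9%), and 6 who leave would all have been non-responders and are left out. The observed rate is 37/51 = 72.5%, a shift of 7.6 points against a 20-point margin. This is a bound, not a forecast: all six would have to look disease-free at exit and fail later.

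**The case against.** The strongest reply is that nothing here orders removal. Section 7.3 is worded permissively, Section 7.4 is largely a list for classifying reasons, and investigator withdrawal is optional. Exit evaluations are required, participants stay in their randomized arm, and Section 12.3 keeps everyone evaluable. All of this stands. A reader might infer that participants must be taken off study and their response discarded, but the documents do not say so. What remains is that they permit the exit, give no later response assessment and no rule for the exit finding.

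A reader might also size the loss from the three Grade 3 events reported at 140 J/cm² in Section 1.5.3 against the 17 SCC lesions treated at that dose. That is not a usable rate. It divides patients by lesions, and the patient denominator is not given. The events were local, whereas the Appendix E scale is for systemic toxicity. They resolved, and nothing says those patients left follow-up.

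A third inference is that the person who withdraws a participant also judges response. Section 7.4 names the investigator; Sections 9.1 and 12.3 name the treating physician. They may coincide, but the documents do not say that they do.

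It is also fair that power loss is modest at low loss rates, and that at one-sided 0.05 power stays above 80% throughout the range shown. Section 4.3 and the exit evaluation would catch PDT failures already visible at exit. The exposure is to failures that come later.

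**Conclusion.** The concern holds as a gap in the rules. The plan needs a 24-month response from all randomized participants, permits exits unrelated to efficacy well before then, and neither continues response follow-up nor says how the exit assessment counts. It should be corrected before outcomes accrue.

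The size cannot be fixed from the documents. Under the assumed 5% to 20% equal loss, and on the assumption of a one-sided 0.025 test, power goes from 81.5% to between 79.3% and 72.4%. The more serious risk is bias from unequal or outcome-related loss; its direction and amount are unknown. The documents do not establish that exits will be frequent, that they will differ by arm, or that removal is compulsory.

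**What to change.** 1. In Sections 7.3 and 7.4, separate the end of treatment from the end of follow-up. State that toxicity, noncompliance and investigator judgment do not end response follow-up; only withdrawal of consent for follow-up, death or true loss of contact does.
2. Collect 24-month disease status at the NCCN visits already scheduled in Section 8.8, or from the clinical record if study visits stop. Add matching consent wording. Appendix A mentions consent to limited participation but does not define it.
3. State that an assessment at early exit is not a 24-month response.
4. Pre-specify how a still-missing 24-month response is counted, for example as non-response in the primary analysis with an observed-case sensitivity analysis. The sentence excluding imputation must be reworded to fit. Non-response counting has its own limit: with equal 10% loss, a true gap of 85% − 65% = 20 points shrinks to 0.9 × 20 = 18, so neither analysis should stand alone.
5. Reconcile the withdrawal reasons for additional therapy and adverse surgical pathology with the drop-and-replace rule in Section 4.3 and with intent-to-treat in Section 12.2.
6. State the sidedness of the non-inferiority test.

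The cost is protocol and consent wording plus some chart abstraction, with no added visits or participants and no change to treatment. Status taken from records may lack the ruler photograph or caliper measure in Section 9.1, so record-based results should be flagged. If all 57 per arm are followed to month 24, power stays at 81.5%.

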7.4 STUDY WITHDRAWAL

Upon participant withdrawal from the study, all end of study evaluations and tests will be conducted. All participants who discontinue due to an AE must be followed until the event resolves or stabilizes. Appropriate medical care should be provided until signs and symptoms have abated, stabilized, or until abnormal laboratory findings have returned to acceptable or pre-study limits. The final status of the AE will be reported in the participant's medical records and the appropriate eCRF.

Reasons for study withdrawal should be classified as follows:

- Death.
- Progressive disease.
- Treatment-related toxicity.
- Toxicity unrelated to treatment.
- Investigator judgment.
- The Investigator may withdraw a participant if, in his/her judgment, it is in the participant's best interest to do so.
- Participant receives an additional adjuvant therapy.
- Noncompliance
- Participant voluntary withdrawal
- A participant may withdraw from the study at any time, for any reason. If a participant discontinues treatment, an attempt should be made to obtain information regarding the reason for withdrawal.
- Participants in which the surgical pathology demonstrates perineural invasion, extracapsular spread or the participant requires additional therapy including radiation or chemotherapy.

Participants who are unavailable for follow-up evaluations should be classified as lost to follow-up for 1 of the following reasons:

- Lost to follow-up: For a participant to be considered lost to follow-up, the investigator must make two attempts to re-establish contact with the participant. The attempts to re-establish participant contact must be documented (e.g., certified letter).
- Death: Date and cause of death will be recorded for those participants who die within 30 days after last dose of study drug (telephone contact with family is acceptable).

8 STUDY PROCEDURES

Unless otherwise defined in the written protocol text, all procedures/assessments will be conducted in accordance with RPCI Clinical Research Services Standard Operating Procedures.

8.1 PARTICIPANT RANDOMIZATION AND REGISTRATION

We will employ a web-based stratified blocked randomization scheme developed at RPCI by the biostatistician in conjunction with the GOG Foundation Statistical & Data Management Center. Participants will be randomized stratified by study site with permuted blocks of size 4 within strata and will assigned to standard of care surgery or PDT with HPPH. Study sites will need to have IRB approval entered into the system prior to accessing the randomization system. Eligibility of each participant will be established prior to randomization.

Informed consent **MUST** be completed prior to receiving any study related procedures.

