4.1 STUDY DESIGN

This is an open-label, randomized, multicenter Phase II study of HPPH-mediated PDT in participants with lesions that are diagnosed as previously untreated T1 N0 or T2 N0 SCC of the oral cavity. Participants will be randomized at a ratio of 1:1, to be treated with either surgery (57 participants) or PDT with HPPH (57 participants). The randomization will be done at RPCI by the biostatistician. The study schema is depicted in **Figure 1**.

Participants will be treated on an outpatient basis. Rarely, those undergoing HPPH with PDT may require hospitalization but this will be decided on a case by case basis. Participants undergoing surgery may be hospitalized.

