4.3 MANAGEMENT OF THE NECK AND SALVAGE SURGERY

The management of the neck will be according to standard of care, at the discretion of the treating surgeon. If the participant, based on the pathology of the neck dissection or primary oral cancer resection, has perineural invasion, extracapsular spread, or requires additional therapies including radiation or chemotherapy, they will be dropped from the study and replaced with another participant.

Participants will receive standard curative therapy 6 weeks after failing to respond to PDT with HPPH. All the participants who will have disease progression, local recurrence, or partial or no response (PR, NR) following the PDT with HPPH will be considered treatment failures. The determination will be performed during the study visits, and based on clinical exam and pathology, if clinical exam is unclear.

The surgeon will provide a surgical plan for every patient, including those randomized to PDT. If the patient requires salvage surgery post-PDT, the surgeon will compare the salvage surgery specimen diameter to the diameter of the spot size used for PDT. This data will be used to demonstrate whether PDT affects the surgical plan.

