4.4 TARGET ACCRUAL AND STUDY DURATION

A maximum of 114 participants at 3 sites, including RPCI, will be enrolled. Accrual is expected to take up to 4 years. Each participant is expected to be on the study for two years and will be followed according to NCCN guidelines.

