3. PARTICIPANT REGISTRATION

The participant, or their legally authorized representative, completes the **Gender, Race, and Ethnicity Form** and this is placed in the study binder.

RPCI does not grant exceptions to eligibility criteria.

Phase 2 Protocol Registration Instructions

The Screening and Enrollment Log must be faxed to the RPCI Network Office within 1 business day of the date the participant is consented. Once the Investigator has determined that eligibility has been met, complete the Subject Registration Form and fax it to the RPCI Network Monitor at [contact].

Protocol Randomization Instructions

4. Patients at Roswell Park Cancer Institute will be registered directly by Roswell staff using the web-based registration system. For patients at institutions outside Roswell Park Cancer Institute, the local site staff will contact the appropriate coordinator to register the patient using the web-based registration application as developed by the GOG Foundation Statistical & Data Management Center in conjunction with the study biostatistician. Within 24 hours the Network Monitor will email the randomization arm assignment and network participant ID # back to the site PI. The site PI will send a confirmation email back to the Network Monitor verifying the randomization arm for the specified network participant. Questions regarding randomization issues can be emailed to [contact] or [contact].

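### One printed block size of 4 within site, in an open-label trial, lets a site know up to about one in three assignments for certain at randomisation

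*Combined protocol and SAP*

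**What the plan says.** Section 8.1 gives one block size and one stratification factor: "Participants will be randomized stratified by study site with permuted blocks of size 4 within strata". Section 12.2 repeats the stratification without a size, "with blocking stratified by clinical site (RPCI, and two other participating sites"). Section 4.1 sets the context: "This is an open-label, randomized, multicenter Phase II study of HPPH-mediated PDT", with 1:1 allocation of 57 and 57. No section provides for varied or undisclosed block sizes.

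Appendix A (Participant Registration) shows how sites learn their assignments. At RPCI, "Patients at Roswell Park Cancer Institute will be registered directly by Roswell staff using the web-based registration system". For the other sites, "Within 24 hours the Network Monitor will email the randomization arm assignment and network participant ID # back to the site PI".

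Three safeguards are written in:
- Allocation is by a central web system (section 8.1).
- Eligibility is settled before randomisation (section 8.1).
- Consent is logged centrally: "The Screening and Enrollment Log must be faxed to the RPCI Network Office within 1 business day of the date the participant is consented".

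Section 4.4 gives the pace: "A maximum of 114 participants at 3 sites, including RPCI, will be enrolled. Accrual is expected to take up to 4 years".

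**The concern.** A block of 4 must hold two assignments to each arm. Anyone who knows the block size and has seen the earlier assignments in the block can sometimes state the next one outright. In an open-label trial the site has seen them, and here the protocol that its investigators hold prints the size.

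A site that knows the next arm could decide whom to approach, or how to settle a borderline eligibility judgement, with that arm in mind. Section 5 leaves eligibility at network sites to the treating physician or a designee. Several criteria in sections 5.1 and 5.2 are matters of judgement, such as accessibility for illumination, life expectancy and the investigator-opinion exclusion.

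T stage and tumor thickness are not stratification factors, and section 12.2 states no covariate adjustment for the primary Farrington-Manning comparison. Neither the design nor that analysis would correct steering on those features. Non-inferiority rests on the PDT-minus-surgery difference, so comparability of the arms is what is at stake.

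**Working it through.** The plan gives no figure for predictability, so there is none to reproduce. Its power statement does not depend on this point.

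**Inputs.** Block size 4 and stratification by site (section 8.1); 1:1, 114 patients (sections 4.1 and 4.4); 3 sites, accrual up to 4 years (section 4.4). Accrual per site and the consent-to-randomisation lag are not given and are assumed below.

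**1. One block of 4.** There are 6 equally likely orderings of two PDT and two surgery. The next arm is certain once one arm is used up.
- Positions 1 and 2: certain in 0 of 6 orderings each.
- Position 3: certain in 2 of 6 (first two alike).
- Position 4: certain in 6 of 6.

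Total: 8 of 6 × 4 = 24 positions, or 33.3%, which is 4/3 per block.

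**2. Over 114 patients.** With 38 per site, each site has 9 complete blocks and 2 patients over: 9 × 4/3 = 12 certain, so 36 of 114 (31.6%). A 58/28/28 split gives 37.3 (32.7%). Guessing the arm with more places left is right 50.0%, 66.7%, 66.7% and 100% of the time by position, an average of 70.8%. With incomplete last blocks this is 70.2% at 38 per site.

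These counts assume exactly 114 randomised. Section 4.3 says of certain participants that "they will be dropped from the study and replaced with another participant". With 6 to 24 extra randomisations (assumed, spread equally) the count is 40 to 44.

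**3. At the moment of approach.** Suppose each patient is randomised a fixed lag L after approach, in order, with Poisson arrivals. The rate is 114/(3 × 48) = 0.79 per site per month. With m patients pending:
- m = 0: as in step 1.
- m = 1: only position 4 can be certain, and only if the first two were alike (1/3 per block).
- m ≥ 2: nothing is certain.

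For 38 per site the share is (12·P0 + 3·P1)/38, where P0 and P1 are Poisson probabilities with mean 0.79 × L/30.4.

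| Lag (assumed) | P0 | P1 | Certain at approach |
|---|---|---|---|
| 7 days | 0.834 | 0.152 | 27.5% |
| 14 days | 0.695 | 0.253 | 23.9% |
| 30 days | 0.458 | 0.358 | 17.3% |
| 45 days | 0.310 | 0.363 | 12.7% |

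**4. Block sizes drawn at random from 4, 6 and 8.** This was simulated for 38 per site, with an observer who knows the set of sizes but not their order. About 2.3% of assignments are certain at randomisation (about 3 of 114), and the best guess is right 67.6% of the time.

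**5. Switching at half accrual (19 per site, assumed).** By then each site has had 4 × 4/3 + 1/3 = 5.67 certain assignments, 17 in all. Under fixed blocks, 36 − 17 = 19 of the remaining 57 would be certain. With the switch, the fourth place of each part-filled block is still certain (3), and the new blocks add about 1.3 over the other 54. That makes about 4 instead of 19.

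**6. Balance.** The largest possible imbalance is half a block: 4 instead of 2 within a site, 12 instead of 6 over three sites. By exact calculation, an overall imbalance above 6 has probability about 0.02%.

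**The case against.** The strongest case is that this is good-practice advice, not an error. Central allocation hides the list, eligibility comes before randomisation, planned accrual is under one patient per site per month, and eligibility is narrow. Steering would mostly mean passing over a patient. All of that stands, and it is why the point is minor. The safeguards still leave a gap. A hidden list does not prevent inference from past assignments, and the log follows consent, so nothing indicates that it records patients who were never approached.

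Three stronger readings are tempting and are not supported.
- *A site knows one in three assignments when choosing whom to approach.* One in three applies at randomisation with nobody pending. Consent and eligibility come earlier, the documents give no lag, and any lag lowers the share.
- *Selection has occurred, or the primary difference is biased by some amount.* The documents give no evidence of steering, no direction and no basis for a size.
- *Varying the blocks makes allocation unpredictable.* It removes nearly all certainty, but a likely arm can also be acted on, and best-guess accuracy falls by only 2 to 3 points.

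**Conclusion.** The point holds as a minor design weakness with an inexpensive remedy. Up to about one in three assignments can be known for certain at randomisation. That is exactly 8 in 24 for complete blocks, and 36 to 37 of 114 under the assumed site splits, provided staff track their own site's assignments. At the point of approach the share is lower, about 27.5% to 13% for assumed lags of 7 to 45 days. Those shares rest on equal sites, Poisson arrivals at the planned rate and first-in, first-out randomisation. The finding describes an opportunity. Its effect on the PDT-minus-surgery difference cannot be estimated from the documents, and the sample size is unaffected.

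**What to change.** If randomisations remain:
- Let each site complete its current block of 4, then draw block sizes at random from 4, 6 and 8 within site.
- Reword section 8.1 to *permuted blocks of varying size, stratified by site*, with no sizes.
- Keep the sizes in a document held by the biostatistician and the data centre, and withheld from all recruiting and treating staff. This must include those at RPCI, which is itself a recruiting site as well as the place where the scheme is developed.

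**Cost.** A protocol revision needing IRB approval before implementation (section 15.1); reconfiguration of a web system built with an outside data centre, whose capabilities the documents do not describe; and the slightly larger possible imbalance in step 6.

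A descriptive comparison of T stage and thickness by arm in the deducible positions already used is not worth relying on. At half accrual there are about 17 such positions. With about 9 per arm, Fisher's exact test (two-sided 0.05, rates centred on 50%) has power of about 7%, 14% and 26% for imbalances of 20, 30 and 40 points, so a clean table would not rule out steering. Omit it, or print its power for the blocks actually used. If accrual is complete, the block change no longer applies, and the fixed block size should be reported as a limitation.
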